#### Treatment Groups [REDACTED]

[REDACTED]

The study consists of a Screening Period [REDACTED] treatment period ([REDACTED] double-blind placebo-controlled treatment period followed by [REDACTED] double-blind active treatment period), and [REDACTED] Observational Safety Follow-up Period.

Part 1: Double-blind placebo-controlled, where subjects will receive either tildrakizumab [REDACTED] (Arm A) or placebo (Arm B) [REDACTED]

Part 2: At Week 16, subjects initially randomized to placebo will be switched over to receive tildrakizumab 100 mg [REDACTED]. Subjects initially randomized to tildrakizumab 100 mg will continue to receive active drug [REDACTED]. In order to maintain the blind, subjects in both treatment arms will receive matching placebo injections at specified time points as described in the SoA.

Part 3: After Week 52 (or early termination of study treatment prior to Week 52), subjects will enter the [REDACTED] Observational Safety Follow-up Period where tildrakizumab treatment will be stopped.

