## 3.0 OBJECTIVES AND ENDPOINTS

Table 1 Study Objectives and Endpoints

Objectives	Endpoints
Primary Efficacy Objective	Primary Efficacy Endpoint

 
To assess the efficacy of tildrakizumab in subjects with moderate to severe scalp psoriasis, as measured by the proportion of subjects who achieve Investigator Global Assessment (IGA) mod 2011 (scalp) score of “clear” and “almost clear” with at least 2-point reduction from Baseline at Week 16.
 
	
 
The proportion of subjects with IGA mod 2011 (scalp) score of “clear” and “almost clear” with at least 2-point reduction from Baseline at Week 16.
 

Primary Safety Objective	Primary Safety Endpoint

 
To assess the safety and tolerability of tildrakizumab in subjects with moderate to severe plaque psoriasis of the scalp [REDACTED] 52 weeks.
 
	
 
The percentage of subjects with incidence, seriousness and severity of all adverse events.
 
The percentage of subjects with severe infections, [REDACTED] whether or not reported as a serious event as per the regulatory definition.
 
The percentage of subjects with malignancies (excluding carcinoma in situ of the cervix).
 
The percentage of subjects with non-melanoma skin cancer.
 
The percentage of subjects with melanoma skin cancer.
 
The percentage of subjects with Major Adverse Cardiovascular Events (MACE).
 
The percentage of subjects with study treatment-related hypersensitivity reactions (eg, anaphylaxis, urticaria, angioedema, etc.).
 
The percentage of subjects with injection site reactions (eg, pain, erythema, edema etc).
 

Secondary Objectives	Secondary Endpoints

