**9.4.2.1 Adverse events and Serious Adverse Events**

Treatment-emergent adverse events are defined as AEs that first occurred or worsened in severity after the first administration of study treatment.

Adverse events will be coded using the Medical Dictionary for Regulatory Activities. For each study treatment, numbers of TEAEs and incidence rates will be tabulated by preferred term and system organ class.

Treatment-emergent AEs by maximum severity, TEAEs by relationship to study treatment, SAEs, TEAEs leading to death, and TEAEs leading to discontinuation of study treatment will be

tabulated for each treatment arm. Commonly occurring TEAEs, [REDACTED] in either treatment arm, will be summarized using descriptive statistics.

The safety of tildrakizumab will be evaluated by and reported as the percentage of subjects for the following TEAEs:

- Incidence, seriousness and severity of all AEs, death cases and discontinuations from the study.
- Percentage of subjects with severe infections, defined as any infection meeting the regulatory definition of a serious adverse event, or any infection requiring IV antibiotics whether or not reported as a serious event as per the regulatory definition.
- Percentage of subjects with malignancies (excluding carcinoma in situ of the cervix).
- Percentage of subjects with non-melanoma skin cancer.
- Percentage of subjects with melanoma skin cancer.
- Percentage of subjects with MACE [REDACTED]
- Percentage of subjects with study treatment-related hypersensitivity reactions (eg, anaphylaxis, urticaria, angioedema, etc).
- Percentage of subjects with injection site reactions (eg, pain, erythema, edema, etc).

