
 
• The Investigator is obligated to assess the relationship between study treatment and each occurrence of each AE/SAE. The AE must be characterized as certainly/definitely related, unrelated, unlikely to be related, possibly related, or probably related. 
 
○ “Certainly/definitely related” suggests that a clinical event, including laboratory test abnormality, occurring in a plausible time relationship to drug administration, and which cannot be explained by concurrent disease or other drugs or chemicals. The response to withdrawal of the drug (de-challenge) should be clinically plausible. The event must be definitive pharmacologically or phenomenologically, using a satisfactory re-challenge procedure if necessary.
 
○ “Probably related” conveys that there are facts, evidence, and/or arguments to suggest a causal relationship, rather than a relationship cannot be ruled out.
 
○ “Possibly related” suggests that the association of the AE with the study treatment is unknown; however, the AE is not reasonably supported by other conditions.
 
○ “Unlikely to be related” suggests that only a remote connection exists between the study treatment and the AE. Other conditions, including chronic illness, progression or expression of the disease state or reaction to concomitant therapy, appear to explain the reported AE.
 
○ “Unrelated” is used if there is not a reasonable possibility that the study treatment caused the AE.
 
 
 
• The Investigator will use clinical judgment to determine the relationship.
 
• Alternative causes, such as underlying disease(s), concomitant therapy, and other risk factors, as well as the temporal relationship of the event to study treatment administration will be considered and investigated.
 
• The Investigator will also consult the IB and/or Product Information, for marketed products, in his/her assessment.
 
• For each AE/SAE, the Investigator must document in the medical notes that he/she has reviewed the AE/SAE and has provided an assessment of causality.
 
• There may be situations in which an SAE has occurred, and the Investigator has minimal information to include in the initial report to [REDACTED]. However, it is very important that the Investigator always make an assessment of causality for every event before the initial transmission of the SAE data to [REDACTED].
 
• The Investigator may change his/her opinion of causality in light of follow-up information and send a SAE follow-up report with the updated causality assessment.
 
• The causality assessment is one of the criteria used when determining regulatory reporting requirements.
 

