763 **4.9.3.3 Interim Analyses (IA), Data Monitoring and Primary Results Reporting**

764 Following the last subject's Week 16 visit, the IA (primary analysis) will be conducted on
765 available data to evaluate efficacy and safety.

[REDACTED]

[REDACTED]

[REDACTED]

[REDACTED]

[REDACTED]

795 **4.9.3.4 Multicenter Studies**

796 Descriptive summaries of the primary and key secondary efficacy endpoints will be presented
797 for each individual study center to evaluate potential heterogeneity across sites.

[REDACTED]

[REDACTED]

[REDACTED]

[REDACTED]

[REDACTED]

810 **4.9.4 Tabulation of Individual Response Data**

811 All efficacy variables will be listed by subject.

812 **4.9.5 Drug Dose, Drug concentration, and Relationships to Response**

813 Not applicable.

814 **4.9.6 By-Subject Displays**

815 No individual subject profile data will be produced.

[REDACTED]

820 **4.10 Safety Analysis**

821 The safety and tolerability of the study drugs will be evaluated by reported adverse events
822 (AEs), physical examinations, electrocardiogram results (ECGs), vital signs, laboratory test
823 results (Hematology, Biochemistry, and Urinalysis), and Columbia-Suicide Severity Rating
824 Scale (C-SSRS).

825 All safety summaries will be based on the Safety Analysis Set.

826 Following reporting of interim Week 16 results, a group comprising formerly placebo-treated
827 subjects who migrate to tildrakizumab 100 mg for the remainder of the study will be
828 identified for reporting at the end of the study.

829 **4.10.1 Adverse Events**

830 The incidence of treatment-emergent AEs (TEAE) will be summarized and tabulated by
831 treatment group, MedDRA (Version 24.0 or higher) System Organ Class (SOC) and
832 Preferred Term (PT). A TEAE is defined as an AE that first occurred or worsened in severity
833 after the first administration of study treatment.

834 Several occurrences of the same AE in one subject will be counted once at the worst severity
835 grade. [REDACTED]
[REDACTED]

837 The relationship of each AE to the study drug will be grouped as related (definitely, probably,
838 possibly related) or unrelated (unlikely to be related, unrelated). Several occurrences of the
839 same AE in one subject will be counted once and the one with the closest relationship to
840 study medication will be counted. If an AE is missing the relationship to study medication,
841 the event will be assumed to be related to study drug for analysis and summarization.

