[REDACTED]

[REDACTED]

848 Non-TEAEs will be listed only and will not be included for analysis and summarization.

849 All AEs will be presented in a by-treatment and by-subject listing, detailing the verbatim
850 term, SOC, PT, application site reaction or not, related to study indication or not, start date,
851 stop date, time since most recent dose of IP, severity, outcome, relationship to study drug,
852 action taken regarding study drug, action taken to treat AE, seriousness and criteria for
853 seriousness. Serious AEs (SAEs) and TEAEs leading to study medication discontinuation,
854 AEs of Special Interest (AESI), and events of clinical interest (ECI) will also be presented in
855 separate listings.

856 An AE profile for the Safety Analysis Set will be provided for Part 1, Parts 2 and 3, and
857 overall, which summarizes the subject incidence, by treatment received for the following
858 information:

- 859 • Any TEAEs;
- 860 • Non-TEAEs;
- 861 • Drug-related TEAEs;
- 862 • Any TEAEs with an outcome of death;
- 863 • Treatment-emergent SAEs;
- 864 • Drug-related treatment-emergent SAEs;
- 865 • TEAEs leading to discontinuation of study medication;
- 866 • Drug-related TEAEs leading to discontinuation of study medication;

- 867 • Any AEs of special interest, including:
868 ○ Injection site reactions
869 ○ Severe infections
870 ○ Malignancies (excluding carcinoma in situ of the cervix).
871 ○ Non-melanoma skin cancer
872 ○ Melanoma skin cancer
873 ○ Major Adverse Cardiovascular Events (MACE)
874 ○ Study treatment-related hypersensitivity reactions.

[REDACTED]

[REDACTED]

891 The number and percentage of subjects with TEAEs will be summarized for each treatment
892 arm and/or in total by SOC and PT. Drug-related TEAEs, TEAEs leading to discontinuation
893 of study drug, drug-related TEAEs leading to discontinuation of study drug, treatment-
894 emergent SAEs, and drug-related treatment-emergent SAEs will be summarized in the same
895 manner. For these summaries, subjects with multiple AEs will be counted only once per SOC
896 and PT.

897 TEAEs by maximum severity and TEAEs by relationship to study treatment, and commonly
898 occurring TEAEs, i.e., those that occur in [REDACTED] of the subjects in either treatment arm,
899 will be summarized by SOC and PT by treatment received in Part 1, Parts 2 and 3, and
900 overall.

901 Injection site reactions will be described in a by-subject listing and may be summarized
902 separately if deemed necessary.

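### The hypersensitivity endpoint is the only specific-event safety endpoint filtered by investigator causality, so reactions judged unlikely or unrelated leave the pooled percentage; an all-causality row is needed

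*Protocol*

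**What the plan says.** Table 1 in Protocol 3.0 lists, among the primary safety endpoints, "The percentage of subjects with study treatment-related hypersensitivity reactions (eg, anaphylaxis, urticaria, angioedema, etc"). The Synopsis and Protocol 8.3.6 carry the same restriction, Protocol 9.4.2.1 repeats it as "Percentage of subjects with study treatment-related hypersensitivity reactions (eg, anaphylaxis, urticaria, angioedema, etc"), and the AESI list in SAP 4.10.1 has "Study treatment-related hypersensitivity reactions". In the list in 9.4.2.1, no other specific event (severe infections, malignancies, the two skin cancer items, MACE, injection site reactions) is limited by causality.

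Causality is assigned by the investigator. Under Assessment of Causality in Protocol Appendix 4, "The AE must be characterized as certainly/definitely related, unrelated, unlikely to be related, possibly related, or probably related", and "The Investigator will use clinical judgment to determine the relationship". SAP 4.10.1 reduces the five levels to two: "The relationship of each AE to the study drug will be grouped as related (definitely, probably" and possibly) on one side, unlikely and unrelated on the other. Two further SAP rules apply. A missing relationship is treated as related, and where the same event recurs in a subject, the occurrence with the closest relationship is counted.

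At Week 16, "subjects initially randomized to placebo will be switched over to receive tildrakizumab 100 mg" (Synopsis, Treatment Groups), while the other arm stays on active drug. SAP 4.10.1 reports the AE profile for Part 1, for Parts 2 and 3 together, and overall. It also plans all TEAEs by SOC and PT, TEAEs by relationship for the same periods, and by-subject listings.

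**The concern.** In a randomized, blinded, placebo-controlled period, the placebo arm already accounts for background urticaria or angioedema. A case-by-case causality filter is not needed for that purpose, and it removes events from an outcome that is likely to be rare. A reaction ascribed to a food or another drug drops out of the one row that brings hypersensitivity terms together at subject level.

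After Week 16 the meaning of the row may also change. In Part 1 a blinded investigator weighs a 1:1 chance that the subject is on placebo. From Week 16 the protocol tells the investigator that everyone is on an active regimen. If that lowers the threshold for calling a reaction related, the percentage rises with no change in true risk. At stake is whether the pooled hypersensitivity percentage can be read as a measure of occurrence, between arms in Part 1 and descriptively across periods.

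**Working it through.** The documents state no hypersensitivity rate, so there is no figure of the plan's own to reproduce. What follows is an illustration under stated assumptions.

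**Inputs from the documents.** About 107 subjects per arm. Part 1 lasts 16 weeks. Part 2 runs from Week 16 to 52 (36 weeks) and Part 3 from Week 52 to 72 (20 weeks), so Parts 2 and 3 together last 56 weeks, or 56/16 = 3.5 times Part 1.

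**Assumed inputs.** All-causality 16-week risk r of 1%, 3% or 5%. Share a judged related: 0.3 to 0.5 in Part 1 and up to 0.9 afterwards. Hazard constant over time, including the off-treatment Part 3.

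**Formula.** Weekly hazard h = −ln(1 − r)/16. Related-only risk over t weeks = 1 − exp(−h·a·t). At t = 16 this is 1 − (1 − r)^a.

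**Step 1: events lost in Part 1.** Subjects missed per arm = 107 × (r − related-only risk).

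| r | a | Related-only risk | Missed of 107 |
|---|---|---|---|
| 1% | 0.5 | 0.50% | 0.53 |
| 1% | 0.3 | 0.30% | 0.75 |
| 3% | 0.5 | 1.51% | 1.59 |
| 3% | 0.3 | 0.91% | 2.24 |
| 5% | 0.5 | 2.53% | 2.64 |
| 5% | 0.3 | 1.53% | 3.72 |

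**Step 2: attribution alone, per 16 weeks.** With the true hazard fixed and a raised from 0.5 to 0.9, the related-only risk goes from 0.50% to 0.90% (r = 1%), from 1.51% to 2.70% (r = 3%), or from 2.53% to 4.51% (r = 5%). The all-causality risk does not move.

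**Step 3: duration alone.** With r = 3% and a held at 0.5, the related-only percentage goes from 1.51% over 16 weeks to 1 − 0.97^(0.5 × 3.5) = 5.19% over 56 weeks. An all-causality percentage would go from 3.0% to 1 − 0.97^3.5 = 10.1%. Removing the filter therefore does not make crude percentages comparable across periods.

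**Step 4: both together.** With r = 3% and a = 0.9 over 56 weeks, the related-only percentage is 9.15%. Of the move from 1.51%, duration accounts for the part up to 5.19% and attribution for the rest. An exposure-adjusted related-only rate (h·a) would still change by 0.9/0.5 = 1.8-fold, whereas an exposure-adjusted all-causality rate (h) would not change.

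**The case against.** The strongest reply is that events judged unrelated leave one row and not the report. All-causality TEAEs by SOC and PT are planned. TEAEs by relationship are planned for Part 1, for Parts 2 and 3, and overall. All AEs are listed, and the incidence of all AEs is itself a primary safety endpoint. A reader might infer that a true signal could not be told from a change in attribution. The documents do not support that, because total and related counts for urticaria or angioedema can be compared within each period. This part of the reply stands. What remains missing is the pooling: separate preferred terms do not give the percentage of subjects with any hypersensitivity reaction.

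A reader might also infer that the randomized comparison is biased. The documents do not support that either. Part 1 is double-blind and is tabulated apart from the later periods, so the loss shown is one of sensitivity.

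A third inference would be that any rise after Week 16 is an artefact of attribution. That goes too far. The shift is a possibility arising from the design, longer observation can by itself produce a larger move (Step 3), and former placebo subjects are exposed for the first time. Part 2 also stays double-blind, with matching placebo injections, so investigators know the regimen but not whether a given injection was active. Safety is analyzed descriptively, and no formal comparison of the periods is planned.

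Finally, text after the SAP's AESI list is blacked out, so it cannot be claimed that no term list exists. It can be said only that every readable statement of the endpoint is related-only. The rules for missing causality and for recurrent events also limit under-counting somewhat.

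**Conclusion.** The point holds as a limitation of the summary that is cheap to repair. As written, the pooled hypersensitivity percentage omits reactions judged unlikely or unrelated, unlike the other specific-event endpoints. In Part 1 the loss is about 0.5 to 3.7 of 107 subjects per arm under the assumed 1% to 5% risk and 30% to 50% judged related. It is small in number but can be half or more of the events on those assumptions.

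After Week 16, attribution is one of three possible contributors to a rise, with duration and first exposure, and the related-only row cannot separate them. The planned tables by term and by relationship allow a partial check. All rates, attribution shares and the constant hazard are assumptions; the definition, the grouping of causality levels and the period lengths come from the documents.

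**What to change.** In the SAP 4.10.1 summary, report the percentage of subjects with any treatment-emergent hypersensitivity reaction regardless of causality. Identify reactions from a MedDRA term list fixed before unblinding, plus the anaphylaxis criteria in Protocol Appendix 5. Present the result for Part 1 and for Parts 2 and 3, with exposure-adjusted rates because of the 16 versus 56 weeks. Show the investigator-related subset as a second row, so that the endpoint as the protocol words it stays visible.

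Record this in SAP 4.13 as a change from the protocol. Confine it to the analysis tables: the AESI definition in Protocol 8.3.6, which carries the requirement to report such events as if they were SAEs, should be left as it is.

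The data are already collected, so no visit or procedure is added. The cost is drawing up the term list, one extra table row, and a somewhat higher reported rate.

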#### **9.4.2.2 Physical Examinations, 12-Lead ECG, Vital Signs and Clinical Safety Laboratory Tests (Hematology, Biochemistry, and Urinalysis)**

Summaries and listings of data for physical examination findings, vital signs, hematology, biochemistry, and urinalysis laboratory tests will be presented. Appropriate descriptive statistics will be summarized for the observed value at each scheduled assessment and for the corresponding change from Baseline.

For hematology and biochemistry tests, listings of subject data will also flag up any abnormal or out-of-range values. Clinically significant changes in the laboratory test parameters will be summarized and listed. Hematology and clinical laboratory data will be reported in System International units.

Descriptive statistics will be used to present the safety outcomes including, physical examination results, weight, body mass index, 12-Lead ECG, vital signs measurements, and clinical laboratory test results.

Change from Baseline will also be summarized for vital signs measurements and clinical laboratory test results.

All ECG data results (normal/abnormal) will be summarized using frequency and percentages. Clinically significant abnormalities will be presented in by-subject listings.

The incidence of treatment-emergent abnormal laboratory, vital sign, and ECG values will also be summarized using descriptive statistics.

**9.4.3 Other Analyses**

No other analyses are planned for this study.

[REDACTED]

[REDACTED]

[REDACTED]

[REDACTED]

**9.5 Interim Analyses**

Following the last subject's Week 16 visit, the IA (primary analysis) will be conducted on available data to evaluate efficacy and safety.

[REDACTED]

The SAP will describe the planned IA (primary analysis) in greater detail.

**9.6 Monitoring Committee**

No external data monitoring committee is constituted for this study.

[Redacted]

[Redacted]

[Redacted]

■

[Redacted]

■

■

■

[Redacted]

■

[Redacted]

■

[Redacted]

[Redacted]

[Redacted]

[Redacted]

[Redacted]

[Redacted]

[Redacted]

[Redacted]

[Redacted]

[Redacted]

[Redacted]

[Redacted]

[Redacted]

[Redacted]

[Redacted]

[Redacted]

[Redacted]

[Redacted]

[Redacted]

[Redacted]

[Redacted]

[Redacted]

[Redacted]

[Redacted]

[Redacted]

[Redacted]

[Redacted]

[Redacted]

[Redacted]

[Redacted]

[Redacted]

[Redacted]

[Redacted]

[Redacted]

[Redacted]

[Redacted]

[Redacted]

[Redacted]

[Redacted]

[Redacted]

[Redacted]

[Redacted]

[Redacted]

[Redacted]

[Redacted]

[Redacted]

[Redacted]

[Redacted]

[Redacted]

[Redacted]

[Redacted]

[Redacted]

[Redacted]

[Redacted]

[Redacted]

[Redacted]

[Redacted]

[Redacted]

[Redacted]

[Redacted]

[Redacted]

[Redacted]

[Redacted]

[Redacted]

[Redacted]

[Redacted]

[Redacted text block]

[Redacted text block]

## APPENDIX 2: REGULATORY, ETHICAL AND STUDY OVERSIGHT CONSIDERATIONS

### Regulatory and Ethical Considerations

- This study will be conducted in accordance with the protocol and with the following:
  - Consensus ethical principles derived from international guidelines including the Declaration of Helsinki and Council for International Organizations of Medical Sciences International Ethical Guidelines.
  - Applicable International Council for Harmonisation Good Clinical Practice (ICH GCP) Guidelines.
  - Applicable laws and regulations.
- The protocol, protocol amendments, informed consent form (ICF), Investigator Brochure, and other relevant documents (eg, advertisements) must be submitted to an IRB/IEC by the Investigator and reviewed and approved by the Institutional Review Board (IRB)/Independent Ethics Committee (IEC) before the study is initiated.
- Any amendments to the protocol will require IRB/IEC and regulatory authority approval, when applicable, before implementation of changes made to the study design, except for changes necessary to eliminate an immediate hazard to subjects.
- The Investigator will be responsible for the following:
  - Providing written summaries of the status of the study to the IRB/IEC annually or more frequently in accordance with the requirements, policies, and procedures established by the IRB/IEC.
  - Notifying the IRB/IEC of serious adverse events (SAEs) or other significant safety findings as required by IRB/IEC procedures.
  - Providing oversight of the conduct of the study at the study center and adherence to requirements of 21 Code of Federal Regulations (CFR), ICH guidelines, the IRB/IEC, European regulation 536/2014 for clinical studies (if applicable), and all other applicable local regulations.
  - After reading the protocol, each Investigator will sign the protocol signature page and send a copy of the signed page to the Sponsor or representative (see [Appendix 20](#)).
  - The study will not start at any study center at which the Investigator has not signed the protocol.

